6.4.3.2 Secondary Objectives Analyses

Secondary Objective: Develop a tailored CDST to improve preventive and acute migraine management strategies.

Phase 3 diary data will be utilized. As described above, random effects logistic models will be used to examine the effects of Group (CDST vs. Headache Education Control), Time, and Group X Time on daily adherence to migraine management strategies. Poisson regression model with log of length of follow-up as offset will be used to examine differences between the groups on total number of nonadherence days at the end of the study.

6.4.3.3 Safety

Safety will be evaluated by:

- 1) Tracking adverse events reported by participants, and collected proactively in bi-weekly check-ins conducted by the research coordinator, as described below; and,
- 2) The unblinded research assistant will monitor symptoms recorded in participant's headache diaries for any unexpected changes in symptoms. Potential adverse events or any other situation requiring reaction management will immediately be reported to the PI. If [name] is unavailable, or if her role as PI would interfere with her ability to assess and intervene with participant distress, [name], Ph.D., clinical psychology and Director of Clinical Training at Ferkauf Graduate School of Psychology, Yeshiva University ([contact]) will assess and determine the best course of action in the case of participant distress.

The unblinded research assistant will collate data regarding adverse events and changes in symptoms by group and provide these data to the Data Safety Monitoring Committee monthly. Any SAEs that are possibly related to the study intervention will be reported to the IRB and NIH within 7 days. All AEs will be compiled and reported to the Einstein IRB and NIH in accordance with the Einstein IRB requirements.

6.4.3.4 Analysis of Subject Characteristics

Demographics (age, gender, and education) will be assessed in the initial assessment via questionnaire. Sampling will be stratified by gender (male n = 30; female n = 70; modeled after population migraine demographics) to permit tests of the association between gender and adherence. Basic descriptive statistics (e.g., means, standard deviations, frequencies) for variables of interest will be computed. Graphical approaches will be used to further explore the data where appropriate.

6.4.4 Subsets and Covariates

Although we hope that the randomization procedure will result in relatively equal groups, we recognize that with a pilot study with such a small sample, it is possible groups will differ on relevant variables. We will evaluate differences between randomized groups on demographics of interest: age, gender, education, and race/ethnicity. Because of the relatively low number of men participating in migraine studies, we will stratify both recruitment and randomization by gender. We will also evaluate baseline differences between randomized groups on adherence outcomes collected during Phase 2, and migraine symptoms (days and severity) collected during Phase 2. If any significant differences are found between the groups, we will run unadjusted and adjusted primary outcome analyses.

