6.1.2 METHOD OF ASSIGNMENT/RANDOMIZATION

A research assistant will randomize 60 people (n = 30 per group) to either the CDST Group or Headache Education Control Group, using block randomization with random size blocks using a computerized random number generator. Randomization will be stratified by gender. This research assistant will have no contact with any participant after he or she is randomized.

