6.4.2 Sample Size Considerations

Based on n=30 subjects in CDST and Headache Education Control groups, and assumptions of dropout rate and correlations as described in the initial phase of the study, we will have 80% power to detect an odds ratio of 1.28 in adherence to migraine management strategies between CDST and Headache Education Control.

For Phase 1b, we would like to estimate satisfaction, usability, and attrition over the course of the month of diary use. In our previous daily diary research, approximately 60% of participants do not continue using headache diary applications after 3 days, and approximately 30% of people adhere to the daily diary for the duration of a 30-day study. Therefore, we hope to obtain information from n=60 people regarding satisfaction and usability at the end of the 30-day period.

For the main phase of the study, based on estimated proportions of 0.37 for stress management, 20% with mood disorder and 30% male, cumulative drop-out rate of 0.073, 0.172 and 0.216 at the end of 1, 2, and 3 month, respectively, from previous studies 1, and assuming correlations of no more than 0.6 among repeated daily migraine management strategies, with n=100 participants, we can detect odds ratios of 1.29 between those with and without mood disorder, 1.26 between female and male, and 1.17 corresponding to 1 SD difference in continuous predictors, with 80% power.

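### The Phase 3 models leave out the gender stratum and Phase 2 adherence, adjust only if a baseline test is significant, and do not name the treatment contrast on which the loss depends

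*Combined protocol and SAP*

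**What the plan says.** **Models.** Section 6.4.3.2 uses Phase 3 diary data and states that "random effects logistic models will be used to examine the effects of Group (CDST vs. Headache Education Control), Time, and Group X Time", the outcome being each day's adherence. It adds: "Poisson regression model with log of length of follow-up as offset will be used to examine differences between the groups". No other term is named for either model.

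**Stratum.** Section 6.1.2: "Randomization will be stratified by gender". Sixty people are randomised, 30 per group.

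**Baseline checks.** Section 6.4.4: "We will evaluate differences between randomized groups on demographics of interest: age, gender, education, and race/ethnicity". It continues: "We will also evaluate baseline differences between randomized groups on adherence outcomes collected during Phase 2", together with Phase 2 headache days and severity. The consequence is: "If any significant differences are found between the groups, we will run unadjusted and adjusted primary outcome analyses".

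**Related facts.** Section 5.3.2 admits to Phase 3 only people who completed Phase 2 with at least 80% of diary entries and whose adherence was under 50% on at least one acute and one preventive behavioural strategy. Section 5.2.1 defines four adherence outcomes: early treatment, avoiding overuse, one behavioural strategy per person (stress, sleep or eating), and preventive medication for those who take it. Section 4.3 makes the CDST pilot a secondary objective, and the potential benefits section (3.3.1) says that it is to yield first estimates of effect size.

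**The concern.** Phase 3 is the only randomised comparison in the study. With 30 people per group it can offer a reasonably precise estimate and one clearly labelled result, and the plan weakens both.

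The measure most likely to predict Phase 3 adherence, the same person's Phase 2 adherence, is collected before randomisation but kept out of the model unless a significance test fires. Under randomisation that test reflects chance. A variable can differ significantly and be irrelevant to outcome, or be strongly prognostic and differ by an amount too small to reach significance.

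Once the trigger fires, two results exist. The plan does not say which of the tested variables enter the second one, and no sentence ranks the two. Section 6.4.3.2 also does not say whether the treatment effect is an average group difference, the group coefficient at some time origin, or the interaction. The benefit of adjustment turns largely on that choice.

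**Working it through.** **The plan's own figure.** Section 6.4.2 gives 80% power for an odds ratio of 1.28 with 30 per group. I used a Wald test on the log odds ratio, with variance 1/(30·e·p1·q1) + 1/(30·e·p2·q2), where e is effective days per person. The reference adherence is 0.37 and follow-up is taken as 90 days. For the repeated days, section 6.4.2 is "assuming correlations of no more than 0.6 among repeated daily migraine management strategies". The detectable odds ratio is 1.17–1.18 for independent days, 1.36–1.39 for first-order autoregressive correlation of 0.6, and 3.24 for exchangeable correlation of 0.6. The correlation structure is not stated, so 1.28 is not reproducible but not shown to be wrong. Nothing below uses it.

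**1. How often the trigger fires.** Section 6.4.4 covers four demographic variables, up to four adherence outcomes and two symptom measures, ten in all. Stratification balances gender, which leaves nine. At 0.05 each (section 6.4.1):
- nine independent tests: 1 − 0.95^9 = 0.37
- six clinical tests correlated at 0.3 or 0.5: 0.35 or 0.32
- the test of one Phase 2 adherence measure alone: 0.05

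**2. What the trigger misses.** The standard error of a baseline mean difference is √(2/30) = 0.258 SD. Significance needs 2.00 × 0.258 = 0.52 SD. The average absolute chance imbalance is 0.258 × √(2/π) = 0.21 SD. The shift in the unadjusted estimate is r times the imbalance. For assumed r from 0.2 to 0.7 this is 0.04–0.14 SD for a typical imbalance and 0.10–0.36 SD for one just under the threshold.

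**3. Average group contrast, person-level summaries.** Adjustment multiplies the variance by 1 − r². From 80% power, the approximation Φ(2.802/√(1 − r²) − 1.960) gives 0.82, 0.90 and 0.98 at r = 0.2, 0.5 and 0.7. Simulation (30 per group, effect 0.736 SD, 40,000 trials per r) gives:

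| Power, % | r = 0.2 | r = 0.5 | r = 0.7 |
|---|---|---|---|
| Always adjusted | 80.9 | 89.5 | 97.3 |
| Adjusted only if the Phase 2 adherence test fires | 79.9 | 81.1 | 81.7 |
| Adjusted if any of nine tests fires | 80.2 | 84.0 | 87.0 |

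The gain over the planned rule is about 1 point at r = 0.2, 5.5–8.4 at 0.5 and 10.3–15.6 at 0.7.

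**4. Poisson comparison.** Simulated with 0.37 adherence, the drop-out in section 6.4.2, entry if Phase 2 adherence is under 50%, 72 recorded days, and an assumed intraclass correlation of 0.3 or 0.6. The sampling SD of the log rate ratio falls by 1–2%, 5–7%, 10–14% and 17–24% at r of about 0.2, 0.4, 0.55 and 0.7.

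**5. Logistic model.**
- With a constant group effect and no time terms, the interval narrows by 3%, 8–9%, 19–20% and 30–31% at the same r values. With 18 observations per person, a low count for early treatment, it narrows by 2–19%. This is not the model in section 6.4.3.2.
- With Time and Group X Time included, the interaction is a within-person contrast, and the random intercept already absorbs the variance that Phase 2 adherence would explain. In a linear random-intercept analogue, the ratio of adjusted to unadjusted standard error for Group X Time is 0.994–1.000. Small logistic runs (12 trials per cell) gave 0.993–0.999 for Group X Time and 0.71–0.95 for the group main effect.

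**6. Error rates.** Under no effect, a fixed trigger rule has type I error of 3.5–4.9%. If either result may be claimed once the trigger fires, it is 4.9–6.2%. With the effect in step 3, the two results disagree on significance in 0.7–2.1% of trials if only the Phase 2 adherence test triggers adjustment, and in 2.1–7.6% if any of nine does.

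**7. Gender.** For the 100-person observational phase, section 6.4.2 says "we can detect odds ratios of 1.29 between those with and without mood disorder, 1.26 between female and male". With 30% male, the variance explained is 0.3 × 0.7 × (ln 1.26)² = 0.0112. Against between-person variance of 1.41 or 4.93 (intraclass correlation 0.3 or 0.6) that is 0.8% or 0.2%.

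**The case against.** The strongest reply is that the gain is uncertain and may be close to nil. It rests on an assumed r. Selecting people with poor Phase 2 adherence can narrow the range and lower r, and at r = 0.2 always adjusting adds about one point of power. No gain was computed for avoiding overuse, which has only about three monthly values. If the treatment effect is Group X Time, the precision argument for the logistic model almost disappears. All of this stands. It limits the size of the benefit, but it does not justify the trigger, and the Poisson comparison and any average group contrast can still gain.

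Three stronger readings are tempting, and the documents do not support them.
- A reader might infer that the planned logistic intervals would narrow by up to 30%. That figure comes from a model without the time terms in section 6.4.3.2.
- A reader might infer that no main analysis exists. Section 6.4.3.2 is the planned analysis for this objective, and section 6.4.4 keeps the unadjusted result in every case, so the unadjusted model reads as the default. Section 6.4.4 also names the candidate variables. What is missing is the choice among them and an explicit ranking.
- A reader might infer serious type I inflation. A fixed rule causes none, and free choice between the two results gives about 5–6%.

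**Conclusion.** The point holds as a gap in specification with a possible loss of precision. The text settles three things: the stratum and Phase 2 adherence are absent from the Phase 3 models, adjustment depends on chance baseline differences, and the adjusted model's covariates are not fixed. Confidence in these is high.

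Confidence in the size of the benefit is lower. It ranges from under 1% in precision (Group X Time, logistic) to about 10–16 points of power over the planned rule (average group contrast, r = 0.7), and it depends on an r that the documents do not give. Gender adds under 1% in precision and belongs in the model because it is the stratum. For a secondary objective in a 60-person pilot this should be changed, because the remedy costs almost nothing. It does not invalidate the trial.

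**What to change.** For each management strategy, prespecify one main Phase 3 logistic model and one Poisson model, each including gender and Phase 2 adherence to the same strategy.
- Measure that covariate on the outcome's own scale: proportion of recorded days for the behavioural strategy, per dose or treated headache for early treatment, the monthly measure for overuse, and users only for preventive medication.
- For the behavioural outcome, also include strategy type (stress, sleep or eating), fixed in both groups before randomisation, and state the reference period of the median used for sleep.
- State the time coding and which contrast is the treatment effect.
- Remove the significance trigger, report baseline comparisons descriptively, and label the unadjusted result a sensitivity analysis.

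The cost is SAP wording and some care in defining the covariates. No new data are needed. The models use one degree of freedom each for gender and Phase 2 adherence, plus two for strategy type in the behavioural models, out of 60 people (fewer for preventive medication users).

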6.4.5 Handling of Missing Data

The random effects logistic model is a kind of generalized linear mixed effects model which can take account of missing data due to drop outs. This type of analysis yields robust estimates even in situations when observations are missing both at random, and not at random.

7. Trial Administration

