5.2 OUTCOME VARIABLES

5.2.1 PRIMARY OUTCOME VARIABLES

The primary outcome variables will be **adherence to acute and preventive migraine management strategies**. All primary outcome variables will be assessed through an electronic headache diary.

Adherence to Acute Migraine Management Strategies.

- a) **Treat Early:** When participants record headache activity, they will record type, timing, and current pain level for each acute medication dose taken. Treating early is operationalized as taking acute medication while the pain is mild.
- b) **Avoid Overuse:** Avoiding overuse is operationalized as taking fewer than 10 triptans and 15 non-specific pain medications (NSAIDs and acetaminophen) per month.

Adherence to Preventive Migraine Management Strategies:

- a) **Adherence to Preventive Behavioral Strategies:** Each participant will record information related to a single strategy: stress management, sleep management, or consistent eating. Participants will record either 1) whether they used a stress management strategy today (assessed each evening; Yes = adherent, No = non-adherent), or 2) when they got in and rose out of bed (consistent bedtime and rise-time; assessed each morning; Within 1 hour of median = Adherent, outside of 1 hr of median = Non-adherent).

Adherent), or 3) whether they ate at least three times that day (consistent eating, assessed each evening; Yes = Adherent, No = Non-adherent).

b) **Adherence to Preventive Medication:** If a participant is taking a preventive medication, they will record whether they took preventive medication each day. Taking preventive medication = Adherent, Not taking preventive medication = Not-adherent.

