6.4.3 Planned Analyses

6.4.3.1 Primary Analyses

Primary Objective: Describe and analyze how individual differences and conditions influence adherence to preventive and acute migraine management strategies.

Phase 2 diary data will be utilized. Random effects logistic models will be used to examine the effects of individual differences (e.g., age and gender) and circumstances (headache days/last 7 days, variations in stress) on daily adherence to migraine management strategies during the initial three-month study period. The random effects logistic model is a kind of generalized linear mixed effects model which can take account of missing data due to drop outs. This type of analysis yields robust estimates even in situations when observations are missing both at random, and not at random. The total number of non-adherence days at the end of follow-up will also be obtained, and the effect of individual characteristics and conditions on the rate of non-adherence will be examined using Poisson regression model with log of length of follow-up as offset.

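### Sections 6.4.3.1 and 6.4.5 call the random effects logistic model robust to data missing not at random; in general it is not, and no sensitivity analysis is planned

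*Combined protocol and SAP*

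**What the plan says.** Section 6.4.5 describes the random effects logistic model as a mixed model that can accommodate dropout, then adds: "This type of analysis yields robust estimates even in situations when observations are missing both at random, and not at random". Section 6.4.3.1 repeats both statements.

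For Phase 2, the primary objective, section 6.4.3.1 uses the model for effects "on daily adherence to migraine management strategies during the initial three-month study period". It adds an analysis of total non-adherent days by "Poisson regression model with log of length of follow-up as offset". For Phase 3, section 6.4.3.2 says "random effects logistic models will be used to examine the effects of Group (CDST vs. Headache Education Control), Time, and Group X Time", with the same kind of Poisson model alongside. Section 6.4.4 plans adjusted analyses if the randomized groups differ significantly at baseline.

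Section 6.4.2 assumes, for the main phase, a "cumulative drop-out rate of 0.073, 0.172 and 0.216 at the end of 1, 2, and 3 month", and sizes the study "assuming correlations of no more than 0.6 among repeated daily migraine management strategies". The Phase 3 power statement rests on "assumptions of dropout rate and correlations as described in the initial phase of the study". Section 5.2.2 lists the share of diary entries completed as a feasibility outcome.

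**The concern.** A random effects logistic model fitted by maximum likelihood gives valid estimates when data are missing at random and the model is correctly specified. When the chance that a day is missing depends on the unrecorded adherence value itself, the model has no general protection. The plan claims that protection as a property of the method and then relies on it: section 6.4.5 contains nothing else on missing data.

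Phase 2 and Phase 3 results would then be reported as protected against a bias that the model does not handle, and no analysis would show how far they depend on the assumption. Phase 2 carries the primary objective, and section 3.3.1 says that the study will supply initial effect sizes for the intervention, so bias in the estimates matters whether or not they reach significance.

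**Working it through.** The claim is qualitative, so there is no stated figure to reproduce. Shifts and logging rates below are my assumptions.

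**1. Does anything else in section 6.4 cover it?** The Poisson offset allows for unequal length of follow-up, not for which days are unrecorded. The adjusted analyses in section 6.4.4 address baseline imbalance. I found no shift, pattern-mixture, selection-model or imputation analysis in section 6.4. A part of the design section (5.1) was not available to me.

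**2. How much is missing?** Cumulative dropout is 0.073, 0.172 and 0.216 (section 6.4.2). With dropout uniform within each month, the mean losses by month are 0.073/2 = 0.0365, (0.073 + 0.172)/2 = 0.1225 and (0.172 + 0.216)/2 = 0.194. Their mean is 0.353/3 = 0.118, so about 11.8% of person-days are lost, before missed entries. Using this for Phase 3 is an inference: the text refers only to an initial phase, which is most naturally Phase 2.

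**3. Selective logging (exact).** For entries missing according to that day's adherence:

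observed OR = true OR × [P(logged | adherent) / P(logged | non-adherent)] in CDST ÷ the same ratio in control.

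- Both arms 0.90/0.70: factor 1.00.
- CDST 0.90/0.70, control 0.90/0.90: factor 0.90/0.70 = 1.29. With the arms reversed it is 0.78.

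Simulated fits (90 days, true OR 1.00, intercept SD 1.0, 3,000 per arm, 6 runs) gave an OR of 0.99 with complete data, 0.99 under missing-at-random dropout, 0.99 with the same selective logging in both arms, and 1.31 with the one-arm pattern.

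The one-arm pattern is strong. At the plan's adherence of 0.37, CDST completion would be 0.37 × 0.90 + 0.63 × 0.70 = 0.774.

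**4. Dropout, if the target is all 90 days.** Take adherence 0.37 (odds 0.587), no group effect before dropout, and a shift of the log-odds after dropout in CDST only. Pooled arithmetic for CDST:

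- Shift −1: later adherence 0.178; average 0.882 × 0.37 + 0.118 × 0.178 = 0.347; odds 0.532; factor 0.587/0.532 = 1.10.
- Shift −2: later adherence 0.074; average 0.335; odds 0.504; factor 1.17.
- Shifts +1 and +2: factors 0.89 and 0.80.

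Simulations of the random-intercept model (intercept SD 0.8, 1.5 and 2.22; 1,000 per arm) gave 1.11–1.12 and 1.19–1.22 for the downward shifts, and 0.90 and 0.81–0.82 for the upward ones. Because dropout accumulates, Group X Time is biased too: over 90 days, a ratio of 1.22–1.23 for −1 and 1.41–1.50 for −2.

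In Phase 2, the same downward shifts confined to the 20% with mood disorder change that odds ratio by 1.11–1.12 or 1.19–1.21, below the plan's stated detectable 1.29.

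**5. Why I give no bias-to-SE ratio.** With 30 per arm, the simulated Group SE ran from 0.22 to 0.60 over intercept SDs of 0.8 to 2.22. The top value treats the plan's 0.6 as a latent-scale correlation. Read as a correlation between daily yes/no values, 0.6 implies an intercept SD of about 3.6, outside that range. The Group X Time SE without a random slope was about 0.21–0.28. An assumed slope SD of 1 raised it from 0.21–0.24 to 0.33–0.40, so any ratio using the model without a slope is an upper bound.

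**The case against.** **The target may not be all 90 days.** The Poisson offset, and the removal in section 6.3.7 of people who start a new migraine medication, fit adherence while followed at least as well. On that reading adherence after dropout is not a missing value, and the factors in step 4 fall away. This stands. The reference to the three-month period in section 6.4.3.1 points the other way, so the plan leaves the question open. Selective logging while followed is unaffected by it.

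**Safeguards.** Diary prompts, payment per entry, contact after two missed days and the 80% diary criteria should limit missing days. They apply alike to both arms, and staff other than the randomizing assistant are unaware of allocation. They reduce the amount missing but do not make what remains ignorable. The 0.774 completion in step 3 is below the 80% that Phase 3 entrants have already shown, and Phase 3 dropout may be below 21.6% for the same reason.

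**Pilot size.** Phase 3 is a pilot with 30 per arm, so sampling error may well exceed the bias. That is fair for Phase 3, but Phase 2 is not the pilot part.

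**Completion is already reported.** Section 5.2.2 does list it. Only the breakdown by time, arm and predictor is new.

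A reader might go further and infer that the Phase 3 result will be biased towards CDST, perhaps by as much as the odds ratio of 1.28 used for its power statement. The documents do not support this. There are possible routes: only CDST participants receive notifications tailored to what they log (section 6.1.4), and the removals in section 6.3.7 may be related to adherence. Neither shows that missingness depends on adherence, differs by arm or runs in one direction. The factor of 1.29 comes from a strong assumed scenario.

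**Conclusion.** The concern holds in a limited form. The robustness statement is wrong as a general property of the model, it appears in two places, and section 6.4 has no analysis that tests it. That conclusion needs no assumption about this trial's missing data.

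The size is illustrative. One-arm post-dropout shifts of 1 to 2 log-odds move the group odds ratio by a factor of about 1.1 to 1.2, or about 0.8 to 0.9 in the other direction, and also bias Group X Time. This rests on a full 90-day target, the Phase 2 dropout pattern and a difference between arms. A shift or selectivity common to both arms would do little or no harm to the group comparison. The point should be fixed before analysis, but it does not call the design or the sample size into question.

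**What to change.** 1. In sections 6.4.3.1 and 6.4.5, replace the sentence with: *valid under missing at random, given a correctly specified model*.
2. State whether the target is adherence over the full three months or while followed. Prespecify one modest sensitivity analysis for the strategies assessed daily (behavioural strategy and preventive medication). It should shift the log-odds of adherence on missing days over a stated range in both directions, for example −2 to +2. Vary the shift by main predictor, such as gender and mood disorder, in Phase 2, and by arm in Phase 3, reporting both Group and Group X Time. If the target is adherence while followed, apply it to missed entries within follow-up only.
3. For Treat Early and Avoid Overuse, report completeness and do not impute non-adherence. Treat Early is defined by doses taken ("Treating early is operationalized as taking acute medication while the pain is mild"), and on a missing day it is unknown whether a dose was taken. Avoid Overuse is a monthly count.
4. Break down the completion rate already listed in section 5.2.2, together with dropout, over time: by main predictor in Phase 2 and by arm in Phase 3.

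The cost is wording in two places, a little extra analysis of data already collected, and one table. The downsides are a less favourable statement about missing data and a shift range that is a matter of judgement.
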